4.2. Participant Dispositions

Participant disposition will be summarized in a table for the Screened population. A disposition of participants includes the number and percentage of participants for the following categories: participants who were screened, participants who were screen failures, participants who completed treatment, participants who permanently discontinued treatment, participants who completed the study, participants who discontinued from the study. All percentages will be based on the mITT population.

The reasons for permanent discontinuation of treatment and study participation will also be summarized in this table. The reason for permanent discontinuation of study participation will be also summarized by study period (Screening Period, Treatment Period) The reason for either discontinuation of study treatment or study participation may include any of the following:

- Adverse Event
- Death
- Protocol Deviation
- Pregnancy
- Non-Compliance With Study Drug

- Withdrawal by Subject
- Physician Decision
- Study Terminated by Sponsor
- Site Terminated by Sponsor
- Study Terminated by IRB / ERB
- Lost to follow up
- Other

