### 5.4. Screen Failures

A screen failure occurs when a participant who consents to participate in the clinical study but is not subsequently assigned to study intervention. A minimal set of screen failure information is required to ensure transparent reporting of screen failure participants to meet the CONSORT publishing requirements and to respond to queries from regulatory authorities. Minimal information includes demography, screen failure details, eligibility criteria, and any SAE.

Individuals who do not meet the criteria for participation in this study (screen failure) may not be rescreened.

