2.1. Multiplicity Adjustment

Multiplicity adjustment will not be implemented in this study.

3. Analysis Sets

For the purposes of analysis, the following analysis sets are defined:

Population/Analysis Set	Description
Screened population	All participants who signed informed consent
Modified intent-to-treat population (mITT)	• All participants who are exposed to at least 1 dose of study intervention
Efficacy Analysis Set (EAS)	• This analysis set will be used to estimate the efficacy estimand for the primary objective, and for all other (secondary, exploratory) endpoints.
	• Data obtained during the treatment period from the mITT population, excluding (1) participants who were inadvertently enrolled* and (2) data after permanent discontinuation of treatment or initiation of prohibited medication.
Safety Analysis Set (SS)	• This analysis will be used to assess the safety of study treatment
	• Data obtained during the Treatment Period from the mITT population, regardless of adherence to treatment or initiation of prohibited medication.

* An inadvertent enroller refers to a subject who does not meet inclusion/exclusion criteria but receives study intervention.

4. Statistical Analyses

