When count data are presented, the percentage will be suppressed when the count is zero in order to draw attention to the non-zero counts. A row denoted "Missing" will be included in count tabulations where specified on the shells to account for dropouts and missing values. The denominator for all percentages will be the number of subjects in that treatment within the analysis set of interest, unless otherwise specified.

The analysis model to make comparisons within treatment relative to continuous measurements assessed over time will be an MMRM with terms for:

- Visits, as fixed effects
- Baseline HbA1c ($\leq 8.0\%$, > 8.0%), as a covariate
- Baseline measurement, as a covariate

For analyses of HbA1c, continuous baseline HbA1c will be included in the model instead of baseline HbA1c category. An unstructured covariance structure will model the relationship of within-participant errors.

Logistic regression may be used to examine the within-treatment effect from baseline at 12 weeks in binary efficacy outcomes. The negative binomial regression model will be used to measure the within-treatment effect of discrete count measures if deemed appropriate.

Summary of intercurrent events:

The number of participants who experience an intercurrent event will be summarized in a table by event type (treatment discontinuation for any reason, or initiation of prohibited medication) and visit. For each visit, the number of intercurrent events which happened before or during the measurements taken on that visit will be calculated, excluding the events which happened during or before the measurements taken at the previous visits.

Furthermore, the number of participants without any intercurrent events will be presented by visit too. At each visit the number and percentage of participants without intercurrent events will be shown.

All analyses will be conducted using SAS Version 9.4 or higher.

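### SAP Section 4.2 bases the screening rows of the disposition table on the mITT population, which by definition excludes screen failures and anyone who leaves before the first dose

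*SAP*

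**What the plan says.** SAP Section 4.2 first fixes who the table covers: "Participant disposition will be summarized in a table for the Screened population". Among the rows that need both a number and a percentage it lists "participants who were screened, participants who were screen failures", followed by rows for completing or permanently discontinuing treatment and for completing or discontinuing the study. It then sets one denominator for the whole table: "All percentages will be based on the mITT population". The next paragraph adds the reasons for discontinuation to the same table, and splits the reasons for leaving the study between the Screening Period and the Treatment Period.

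The two populations are defined in SAP Section 3 (and identically in Protocol Section 9.2):

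- Screened: "All participants who signed informed consent".
- mITT: "All participants who are exposed to at least 1 dose of study intervention".

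Protocol Section 5.4 defines the group in between: "A screen failure occurs when a participant who consents to participate in the clinical study but is not subsequently assigned to study intervention".

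SAP Section 4.1 has a general default: "The denominator for all percentages will be the number of subjects in that treatment within the analysis set of interest, unless otherwise specified".

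**The concern.** A percentage in a disposition table should be a part divided by the whole that contains it. Here the table is drawn for one population, and every percentage in it is divided by the size of a smaller one. That is right for the treatment rows, where everyone counted has been dosed. It is wrong for the screened row, the screen-failure row and the Screening Period reasons, because those rows count people who are outside the denominator.

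What is at stake is the descriptive account of participant flow. A screened row above 100% is plainly odd and would probably be noticed. An inflated screen-failure percentage is less conspicuous: a figure of 25% or 43% looks ordinary and gives no hint that it was divided by the wrong count.

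**Working it through.** **Is there a figure in the plan to reproduce?** Not on this point. Neither document gives an expected number screened or a screen-failure rate. The only related number is the planned enrolment of about 150 (Protocol synopsis, SAP Section 1.2). It serves below as an illustrative mITT size, and the percentages do not depend on it.

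**Step 1: can a screen failure be in mITT?** No. A screen failure has consented but is not assigned to intervention (Protocol Section 5.4). Only enrolled participants may receive study intervention (Protocol Section 6.2). Membership of mITT needs at least one dose. A participant who fails the criteria but is dosed anyway is not a screen failure; SAP Section 3 calls that person an inadvertent enroller. Screen failures and mITT are therefore disjoint.

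**Step 2: can a Screening Period discontinuation be in mITT?** No. The Screening Period runs from Visit 1 to Visit 2 (SAP Section 1.2), and the first dose is given at Visit 2 after the baseline procedures (Protocol Section 4.1.1).

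**Step 3: does the general default rescue the table?** No. The rule in SAP Section 4.1 gives way where something else is specified, and Section 4.2 specifies mITT for all percentages without exempting any row.

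**Step 4: the arithmetic.** Let S be the number screened, M the number in mITT, and F the number of screen failures.

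- Screened row as written: S/M = 1 + (S - M)/M. This exceeds 100% whenever S - M is at least 1.
- Screen-failure row as written: F/M = (F/S) × (S/M). The proper rate F/S is multiplied by S/M, so it is overstated whenever F > 0.
- If every undosed participant is a screen failure, then S = M + F. With f = F/S, we have S = M/(1 - f), S/M = 1/(1 - f) and F/M = f/(1 - f).

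With M = 150 and assumed values of f:

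| Assumed true rate f | S = 150/(1 - f) | Screened row, S/M | Screen-failure row, F/M | Screen failures over Screened, F/S |
|---|---|---|---|---|
| 0% | 150.0 | 100.0% | 0.0% | 0% |
| 10% | 166.7 | 111.1% | 11.1% | 10% |
| 20% | 187.5 | 125.0% | 25.0% | 20% |
| 30% | 214.3 | 142.9% | 42.9% | 30% |
| 40% | 250.0 | 166.7% | 66.7% | 40% |
| 50% | 300.0 | 200.0% | 100.0% | 50% |

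Above a true rate of 50% the screen-failure row itself passes 100%. With no undosed participants nothing is distorted, as the first line shows.

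**Step 5: would deleting the sentence be enough?** No. The default would then put every row over the Screened population. At f = 30%, even if all 150 dosed participants completed treatment, the completion row would read 150/214.3 = 70%. The denominator has to be set row by row.

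**The case against.** The strongest objections concern consequence, not the reading of the text.

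- **Counts appear beside the percentages.** Section 4.2 asks for both, so a reader can recompute the right rate, and a screened row above 100% signals the fault. This stands, and it limits the harm.
- **The table shells are a separate document** (SAP Section 1) and could not be checked. They may print no percentage on these rows, or use another denominator. SAP version 2.0 also follows a dry run. This stands as a limit on what can be claimed about the final output. It does not cure the SAP: the listed version 2.0 changes do not include Section 4.2, and if the shell differs, the sentence and the shell conflict.
- **The sizes rest on chosen inputs.** This stands. The rates are assumed, and the f/(1-f) form also assumes that every undosed participant is a screen failure. The direction needs only one undosed participant for the screened row and one screen failure for the screen-failure row.
- **No inference depends on this table.** This stands without reservation.

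A reader might go further and infer that the trial will publish wrong screen-failure rates and so fall short of the CONSORT reporting that the protocol cites. The documents do not support that. Protocol Section 5.4 links CONSORT to a minimum set of information on screen failures (demography, failure details, eligibility criteria and any SAE), not to this table or to any percentage. Nothing says that the screen-failure percentage will be published.

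**Conclusion.** The denominator rule in SAP Section 4.2 is wrong as written for three sets of rows: screened, screen failures, and Screening Period reasons for leaving the study. The cause is a stated rule that contradicts the table's own population, not a missing detail.

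The factor of overstatement on the screen-failure row is S/M, or 1/(1 - f) if all undosed participants are screen failures; a true 30% would be shown as 43%. The size in this trial cannot be known from the documents. Given the HbA1c, BMI, stable-dose, laboratory and retinal entry criteria in Protocol Sections 5.1 and 5.2, at least one screen failure is very likely.

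The point is minor and purely descriptive. The treatment rows already have a suitable denominator. The primary MMRM, the efficacy and safety analysis sets, power and type I error are untouched.

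**What to change.** Replace the denominator sentence in SAP Section 4.2 with row-specific wording, for example:

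> Percentages for the screened, screen-failure and Screening Period discontinuation rows will be based on the Screened population. Percentages for treatment completion and discontinuation, study completion and Treatment Period study discontinuation, with their reasons, will be based on the mITT population.

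The row for discontinuing the study needs one further decision, because it spans both periods and neither denominator suits it as it stands. Report it by period, and restrict the mITT-based row to dosed participants. State also whether Screening Period discontinuations are counted within the screen failures or separately, so that the screening rows add up.

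The cost is a short SAP text change and a check of the disposition shell against it. It needs no new data and changes no inferential analysis.

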4.3. Primary Endpoint Analysis

4.3.1. Definition of endpoint

The primary endpoint for this study is change from baseline in HbA1c at Week 12. This endpoint will be used to evaluate the primary objective of the study.

4.3.2. Main analytical approach

The primary objective based on the efficacy estimand defined in Section 1.1 will be evaluated using the EAS dataset (Section 3). The primary analysis model for HbA1c measurements over time will be a mixed model for repeated measures (MMRM).

The observed changes in HbA1c level from baseline (Visit 2 on Week 0) to each of the scheduled post-baseline visits (Visit 3 on Week 4, Visit 4 on Week 8, and Visit 5 on Week 12) of each participant are the dependent variable. The baseline HbA1c value is incorporated as a covariate, and the visits are treated as fixed effects.

Mean change from baseline at Week 12 will be estimated by least square means (LS means), with accompanying P-value and 95% CI.

Operationally, the hypothesis defined in Section 2 will be tested at a two-sided 0.05 level by performing the test on the least square mean of changes from baseline at Week 12.

An unstructured covariance pattern will be used to estimate the variance-covariance of the withinparticipant repeated measures. Parameters will be estimated by REML with the Newton-Raphson algorithm and using the Kenward-Roger method for calculating the denominator degrees of freedom.

In case the model fails to converge, the following covariance structures will be tested in the following order:

- 1. Heterogenous Toeplitz
- 2. Heterogeneous First Order Autoregressive
- 3. Heterogeneous Compound Symmetry
- 4. Toeplitz
- 5. First Order Autoregressive, and
- 6. Compound Symmetry

The first covariance structure that converges will be used.

Missing data will not be imputed because the maximum likelihood estimate is unbiased for this model in case of a Missing at Random (MAR) mechanism. The P-value obtained for the least

square means for change from baseline will be used to determine the statistical significance to achieve the primary objective.

HbA1c values and change from baseline in HbA1c will also be summarized by visit using descriptive statistics.

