# 9.3. Statistical Analyses

#### 9.3.1. General Considerations

Statistical analysis of this study will be the responsibility of Lilly or its designee.

Any change to the data analysis methods described in the protocol will require an amendment ONLY if it changes a principal feature of the protocol. Any other change to the data analysis methods described in the protocol, and the justification for making the change, will be described in the statistical analysis plan or clinical study report. Additional exploratory analyses of the data will be conducted as deemed appropriate.

All tests of treatment effects will be conducted at a 2-sided alpha level of 0.05/1-sided alpha level of 0.025, unless otherwise stated, and all confidence intervals will be given at a 2-sided 95% level.

Baseline is defined as the last non-missing measurement recorded on or before the treatment initiation visit, prior to first dose of treatment, unless otherwise specified.

Analyses will use the EAS population set to evaluate the efficacy estimand.

Summary statistics for continuous measures may include sample size, mean, standard deviation, median, minimum, and maximum. The analysis model to make comparisons within treatment relative to continuous measurements assessed over time will be an MMRM with terms for:

- visit
- country
- baseline HbA1c (≤8.0%, >8.0%), and
- baseline measurement as a covariate.

For analyses of HbA1c, continuous baseline HbA1c will be included in the model instead of baseline HbA1c category. An unstructured covariance structure will model the relationship of within-participant errors.

Summary statistics for categorical measures, including categorized continuous measures, will include sample size, frequency, and percentages. Logistic regression may be used to examine the treatment effect from baseline at 12 weeks in binary efficacy outcomes. The negative binomial regression model will be used to measure the within treatment effect of discrete count measures if deemed appropriate.

Adjustments to the planned analyses are described in the final clinical study report or in the SAP.

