# 9.3.2. Primary Endpoint Analysis

The primary endpoint for this study is change from baseline in HbA1c at Week 12. This endpoint will be used to evaluate the primary objective of the study (Section 3).

The null hypothesis corresponding to the primary objective is specified in Section 9.1.

The primary objective based on the efficacy estimand defined in Section 3 will be evaluated using the EAS dataset (Section 9.2). The primary analysis model for HbA1c measurements over time will be an MMRM. The response variable of MMRM will be change in HbA1c values from baseline obtained at each scheduled postbaseline visit. The independent variables of the MMRM model are visit, and country as fixed effects and baseline HbA1c as covariates. Missing data will be addressed by the MMRM model. No explicit imputation methods for missing data will be employed. The *P* values obtained for the least square means for change from baseline will be used to determine the statistical significance to achieve the primary objective.

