### 9.3.5.3. Central Laboratory Measures and Vital Signs

Values and changes from baseline to postbaseline values of appropriate central laboratory measures and vital signs will be summarized at each scheduled visit.

The analysis model to make comparisons within treatment relative to continuous change from baseline values assessed over time will be an MMRM, with terms: visit, country, and baseline measurement as covariates.

An unstructured covariance structure will model relationship of within-participant errors.

The percentages of participants with treatment-emergent abnormal, high, or low laboratory measures at any time will be summarized.

A treatment-emergent abnormal value is defined as a change from normal value at baseline to an abnormal value at any time during the follow-up.

A treatment-emergent high result is defined as a change from a value less than or equal to the high limit at baseline to a value greater than the high limit at any time during the Treatment and Follow-Up periods.

A treatment-emergent low result is defined as a change from a value greater than or equal to the low limit at baseline to a value less than the low limit at any time during the Treatment and Follow-Up periods.

High and low limits will be provided in SAP.

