4.5.1. Summary for the Analysis of Exploratory Measures

Objective	Relative to the efficacy measure	Analysis Conducted	Additional information
CGM parameters	Mean change in	MMRM model as	MMRM with terms for:
	TIR from baseline	specified in Section 4.3.2	• Visit
			• Baseline HbA1c category (≤8.0%, >8.0%), and
			• Baseline TIR as a covariate
CGM parameters	Mean change in	MMRM model as	MMRM with terms for:
	TBR from baseline at week 12	specified in Section 4.3.2.	• Visit
			• Baseline HbA1c category (≤8.0%, >8.0%), and
			• Baseline TBR as a covariate
CGM parameters	Mean change in TITR from baseline at week 12	MMRM model as specified in Section 4.3.2 .	MMRM with terms for:
			• Visit
			• Baseline HbA1c category (≤8.0%, >8.0%), and
			• Baseline TITR as a covariate
CGM parameters	ters Mean change in GV MMRM model as specified in		Separate MMRM model for all measures of GV.
	week 12	Section 4.3.2.	MMRM with terms for:
			• Visit
			• Baseline HbA1c category (≤8.0%, >8.0%), and
			• Baseline GV measure as a covariate
CGM parameters	Change in odds for reaching composite	Logistic regression model as specified	Logistic Regression with terms for:
	endpoint of all in ranges from baseline to week 12	in Section 4.5	• Visit

Table 3.	Exploratory measures not controlled for Type 1 error
----------	--

			 Baseline HbA1c category (≤8.0%, >8.0%), and Baseline composite endpoint as a covariate
CGM parameters	Mean change in mean 24-hr daily blood glucose from baseline at week 12	MMRM model as specified in Section 4.3.2.	 MMRM with terms for: Visit Baseline HbA1c category (≤8.0%, >8.0%), and Baseline mean 24-hr daily blood glucose as a covariate
CGM parameters	Mean change in estimated post- prandial glucose excursion from baseline at week 12	MMRM model as specified in Section 4.3.2.	 MMRM with terms for: Visit Baseline HbA1c category (≤8.0%, >8.0%), and Baseline estimated post-prandial glucose excursion as a covariate
CGM parameters	Mean change in estimated fasting glucose at week 12	MMRM model as specified in Section 4.3.2.	 MMRM with terms for: Visit Baseline HbA1c category (≤8.0%, >8.0%), and Baseline estimated fasting glucose as a covariate

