- A treatment-emergent high result is defined as a change from a value less than or equal to the high limit at baseline to a value greater than the high limit at any time during the Treatment and Follow-up periods.
- A treatment-emergent low result is defined as a change from a value greater than or equal to the low limit at baseline to a value less than the low limit at any time during the Treatment and Follow-up periods.
 - Laboratory normal ranges will be provided by the Central Lab.

An MMRM using REML model will be used to analyze the changes in lipid panel parameters from baseline to all scheduled post-baseline visits. The model will include visits and baseline HbA1c category ($\leq 8.0\%$, >8.0%) as fixed effects and baseline value of the dependent variable as a covariate.

Vital signs:

Summary tables presenting observed values and changes from baseline will be presented for vital sign data, *systolic blood pressure (mmHg), diastolic blood pressure (mmHg), pulse rate (bpm),* weight (kg), Waist Circumference measurement (cm) and BMI for participants in the Safety set. For height (cm), only observed values will be summarized at baseline.

Height and weight measurements will be used to calculate BMI, with following formula:

 $BMI = weight (kg) / [height (m)]^2$

Descriptive summaries by nominal visit will be provided for baseline and postbaseline values as well as change from baseline values. If 2 records are taken at the same visit, they will be averaged prior to being used for data summaries and analyses.

An MMRM using REML model will be used to analyze the changes in vital signs from baseline to all scheduled post-baseline visits. The model will include visits and baseline HbA1c category ($\leq 8.0\%$, >8.0%) as fixed effects and baseline value of the dependent variable as a covariate.

Counts and percentages of patients with treatment-emergent abnormal sitting systolic blood pressure (BP), sitting diastolic BP, and pulse will be presented. The criteria for identifying patients with treatment-emergent vital sign abnormalities are stated in Table 4.

Table 4.Categorical Criteria for Abnormal Treatment-Emergent Blood Pressure and
Pulse Measurement

Parameter	Low	High
Systolic BP (mm Hg) (Supine or sitting – forearm at heart level)	Observed value ≤ 90 and decrease from baseline ≥ 20	Observed value ≥ 140 and increase from baseline ≥ 20

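### The SAP drops the protocol's country term and adds an HbA1c term to the safety models while stating that nothing changed; Week 4 TAR reporting and the 189 mg/dL TIR bound also need correcting

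*SAP*

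**What the plan says.** **Model terms.** The protocol lists country in three MMRMs.

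- Primary (9.3.2): "The independent variables of the MMRM model are visit, and country as fixed effects and baseline HbA1c as covariates".
- General (9.3.1): visit, country, the category "baseline HbA1c (≤8.0%, >8.0%), and" the baseline value of the measure.
- Laboratory and vital signs (9.3.5.3): "will be an MMRM, with terms: visit, country, and baseline measurement as covariates".

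The SAP lists country in none.

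- General (4.1): the list introduced by "The analysis model to make comparisons within treatment relative to continuous measurements assessed over time will be an MMRM with terms for" holds visits, baseline HbA1c category and baseline measurement.
- Primary (4.3.2): "The baseline HbA1c value is incorporated as a covariate, and the visits are treated as fixed effects".
- Secondary (4.4.2, Table 2): visits, HbA1c category and baseline value.
- Exploratory (4.5.1): the TIR row, for example, has visit, HbA1c category and "Baseline TIR as a covariate".
- Lipids and vital signs (4.6.4.1): "An MMRM using REML model will be used to analyze the changes in lipid panel parameters", and likewise for vital signs. In both, "The model will include visits and baseline HbA1c category", plus the baseline value.

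Protocol 9.3.1 and SAP 4.1 let the sponsor change a method that is not a principal feature, provided the change and its justification appear in the SAP or the study report. SAP 1 and SAP 4.9 each declare that the protocol's analyses are unchanged.

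**TAR.** The objective in protocol 1.1 and 3 and in the SAP 1.1 table names Week 4 and Week 12. The endpoint text below that table, SAP 4.4.1 and Table 2 name Week 12 only.

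**TIR.** Protocol 3 and SAP 1.1 give 71 to 180 mg/dL. SAP 4.5, where the variable is derived, gives 71 to 189 mg/dL. All three pair the upper bound with 10 mmol/L.

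**The concern.** The protocol and the SAP specify different models for the Week 12 HbA1c LS mean and its P-value, which decide the primary objective. A reader who goes to SAP 4.9 to learn whether the analysis moved is told that it did not. In an open-label, single-arm trial, the value of the plan lies largely in having one model fixed in advance.

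The other two items could affect results if the SAP were followed to the letter. A time point named in a secondary objective could go unreported. TIR could also be computed over a range that overlaps TAR.

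**Working it through.** **1. The plan's own power figure.** Inputs from protocol 9.5 and SAP 5: n = 150, difference 0.3, variability 1.1 (read here as the SD of the change), two-sided 0.05, one-sample t-test. No dropout is assumed.

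SE = 1.1/√150 = 0.0898. Power (noncentral t, 149 df) = 91.3%. This agrees with the stated figure of at least 90%, and it is the precision of a model without country.

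**2. Country added, LS means at observed margins.** Country sizes are not given. Assume 100/30/20, with the largest country differing from the others by 0.3 points.

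- With complete data, the visit terms force the residuals to sum to zero at each visit. The Week 12 LS mean at observed margins is then the observed mean, with or without country.
- Between-country variance = (2/3)(1/3)(0.3²) = 0.020. Residual SD = √(1.21 − 0.02) = 1.091, SE = 0.0891, power (147 df) about 92%.
- With assumed dropout of 5% in the largest country and 25% elsewhere, the two estimates differed by 0.002 points on average and by at most 0.009 in 400 simulated trials (three visits, known covariance).

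**3. Country added, equal country weights.** Same assumed sizes.

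- Shift of the mean = (100/150 − 1/3) × 0.3 = 0.10 points. With three equal countries of 50 the shift is zero.
- SE = (1.1/3) × √(1/100 + 1/30 + 1/20) = 0.112. Power for a true mean of 0.3 = about 76%, with no variance credited to country.

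**4. TAR at Week 4.** SAP 4.4.2 applies the 4.3.2 approach, which models change at every scheduled post-baseline visit, and Table 2 has a visit term. CGM sessions precede Visits 3 and 5 (protocol 8.1.2). The model therefore already yields a Week 4 LS mean. SAP 4.5 summarizes its measures at both weeks, but TAR enters that list only as a component of the composite.

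**5. TIR bound.** At 18.016 mg/dL per mmol/L, 180 mg/dL is 9.99 mmol/L and 189 is 10.49, so 189 does not fit the 10 mmol/L beside it. TAR starts above 180, so readings of 181 to 189 would count in both. Assume normal glucose; the inflation of the TIR level is P(180 < X ≤ 189):

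| Mean / SD (mg/dL, assumed) | Points added to TIR |
|---|---|
| 180 / 50 | 7.1 |
| 170 / 45 | 7.6 |
| 160 / 45 | 6.9 |
| 150 / 40 | 6.2 |
| 140 / 35 | 4.6 |

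The error in the change is the later row minus the earlier row. Over the ten falling pairs it runs from +0.4 (180 to 170) to −3.0 (170 to 140); the smallest in size is 0.3 (180 to 160).

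Composite: TBR below 4% and TAR below 25% leave more than 100 − 4 − 25 = 71% in 71 to 180 mg/dL. The TIR condition of more than 70% is then met under either bound.

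**The case against.** The sponsor may change the model, and protocol 9.3.1 allows disclosure in the study report as well as the SAP. That stands: leaving country out is not a breach in itself. It does not rescue SAP 1 and 4.9, which deny any change, and a later report that disclosed it would contradict them. The pooling of data across centers in SAP 4.1 does not announce the removal either, because the protocol's model also pools the data while adjusting for country. The SAP's revision history is silent on it.

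The effect is also negligible if LS means are taken at observed margins. That stands too. A reader might infer that the primary result is biased or underpowered without country; steps 1 and 2 give no support for that.

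A reader might take the HbA1c category in SAP 4.6.4.1 as a contradiction within the protocol, since 9.3.1 lists it and 9.3.5.3 does not. But 9.3.1 is the general model and 9.3.5.3 the specific one for laboratory measures and vital signs. A specific model that narrows a general one is not a contradiction. The SAP has added a term.

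A reader might infer that Week 4 TAR has no analysis at all. The objectives table keeps the week and the by-visit model produces the estimate, so only the commitment to report it is missing.

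Finally, 189 is probably a typing error in an exploratory endpoint, and its size above rests wholly on assumed distributions. A reader might expect the composite to change as well; step 5 shows that it does not.

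**Conclusion.** The point holds as a documentation defect that should be fixed. The SAP makes two undeclared departures from the protocol: country is removed from every MMRM, and an HbA1c category is added to the lipid and vital-sign MMRMs. Its two no-change statements are therefore false. No harm to the primary estimate or its power is shown, and the real effect of country cannot be known because neither document gives country numbers or sizes.

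The choice of LS-mean weights is what could matter if country returns. The shift of 0.10 points and the fall in power from about 91% to about 76% apply to equal weights under the sizes and country difference assumed above, with SD of change 1.1 and no dropout.

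The Week 4 TAR gap and the 189 mg/dL bound are minor text corrections and do not add to the weight of the main point. Programmed literally, the bound would inflate the TIR level by about 4.6 to 7.6 points. It would put an error of about 0.3 to 3.0 points in the change, usually understating the gain.

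**What to change.** - **Country.** Either restore it as a fixed effect in the SAP MMRMs (4.1, 4.3.2, 4.4.2, the MMRM rows of 4.5.1, and 4.6.4.1) with LS means at observed margins, or declare and justify its removal in SAP 4.9. Observed margins would be new text. They keep the estimate a mean over the enrolled population.
- **HbA1c category in SAP 4.6.4.1.** Declare and justify it in 4.9, or remove it.
- **SAP 1 and 4.9.** Correct the no-change statements for any departure that is kept.
- **TAR.** Add Week 4 for both TAR endpoints in the SAP 1.1 endpoint text, 4.4.1 and Table 2, estimated from the same MMRM.
- **TIR.** Change 189 to 180 mg/dL in SAP 4.5.

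The cost is SAP wording and, if country is restored, one model term and one LS-mean option. No new data are needed.
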